9.8.1. Pregnancy reporting whilst participating in the trial

Pregnancy, or the pregnancy of a partner occurring whilst participating in the trial, is not considered an SAE, however, a congenital anomaly or birth defect is. Other cases (e.g. termination of pregnancy without information on congenital malformation, and reports of pregnancy exposure without outcome data) should not normally be reported as such. When pregnancy occurs in the trial, either in a female participant or the female partner of a male participant, this should be followed up until at least the end of pregnancy, whether that is a live birth, abortion etc. Information on a pregnancy in a trial participant will be captured on the SAE Report Form. Congenital anomalies or birth defects are considered an SAE and so these events must also be reported to the CTO. Congenital anomalies or birth defects related to the IMP and unexpected with respect to the IMP Reference Safety Information (RSI) must be submitted by the CTO within expedited SUSAR time frames (7 or 15 days) to the MHRA, relevant REC and the drug manufacturer of the IMP (to comply with any contractual agreement).

9.9. Premature Termination of the Trial

The trial may be prematurely discontinued by the Sponsor, Chief Investigator or Regulatory Authority on the basis of new safety information or for other reasons given by the Data Monitoring & Ethics Committee.

If the trial is prematurely discontinued, active participants will be informed and no further participant data will be collected. The Competent Authority and Research Ethics Committee will be informed within 15 days of the early termination of the trial.

10. Statistics

The study will use a Simon's two-stage design to assess the efficacy of blinatumomab in patients with molecular relapse or molecular persistence of acute myeloid leukaemia (AML) with a t(8;21). This type of AML has a relatively good prognosis. The study primarily wants to establish activity and early efficacy from the first cycle of blinatumomab. The first group of patients will be recruited at stage I, and if the success criteria are met, the study will proceed to stage II where the second group will be recruited. Safety will be assessed in terms of grade 3+ toxicity, and excessive toxicity will be monitored and assessed regularly through follow-up visit that will be performed at 90 days after the end of infusion with blinatumomab.

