5.5. Dosing Regimen

Patients will receive one to four consecutive cycles of blinatumomab. A cycle consists of a continuous intravenous infusion at a dose of 28 mcg/day over four weeks followed by an infusion free interval of two weeks. Patients will receive four cycles of treatment, unless criteria for treatment discontinuation apply. The duration of one cycle is 6 weeks, including a four week continuous intravenous infusion and a two week infusion free interval, which may be extended by a maximum of 7 days. In case of haematological relapse, the study treatment will be permanently discontinued. Patients are generally are expected to receive four cycles of treatment, independently from achieving complete molecular response. If patients are suitable for allogeneic HSCT after treatment with at least one treatment cycle of blinatumomab, they may undergo allogeneic HSCT instead of receiving further cycles with blinatumomab. Following the last treatment cycle, there will be a safety follow-up visit at 90 days after last infusion, documented as End-of-Core-Study Visit, followed by efficacy follow-up visits at three, six, nine, 12, 18 and 24 months after treatment start. Efficacy follow-up visits at six months will only be applicable for patients completing less than 4 cycles, at three months only for patients having completed 1 cycle only.

After completion of the two year efficacy follow-up period, information concerning haematological relapse free, leukaemia treatment free and overall survival as well as further data on hospitalisation and the use of relevant anti-leukemic, antibiotic, and antifungal medication and transfusion of blood products, and hospitalisation, if available, will be gathered by telephone at least every six months until death or at least until five years after treatment start, whichever occurs earlier. Patients who discontinue treatment prematurely

will enter immediately the efficacy and/or survival follow-up study. Patients who discontinue treatment before completion of the first treatment cycle will be assessed for MRD response on day 29 (and day 43, if applicable) of cycle 1 before entering the efficacy and/or survival follow-up study. In case of haematological relapse within the treatment period, treatment will be terminated at the time of relapse.

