6.7. Expected Duration of Trial

The trial is expected to take 3 years to complete. The end of trial will be defined as the time of database lock.

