7.3. Follow-up Period

7.3.1. 90-day Safety Follow-up Visit

A Safety follow-up visit will be performed at 90 days after the end of infusion with blinatumomab. In case an allogeneic HSCT is planned following treatment with blinatumomab, the 90-day Safety Follow-Up Visit should be performed at the latest possible timepoint prior to the initiation of transplant conditioning, even if the 90 days have not elapsed. This visit will also be documented as End-of-Core-Study Visit and the following procedures and tests will be performed:

- Physical examination and ECOG performance status
- Neurological examination
- Writing test
- Vital signs/temperature
- 12-lead ECG
- Routine bloods, U/E, LFTs, LDH, Coagulations screen, FBC (aproximately 30mL of blood)
- Urinalysis
- Pregnancy test (in women of childbearing potential)
- Serum immunoglobulins (IgG)
- Concomitant medication
- AE/SAE assessment

7.3.2. 2-Year Efficacy Follow-up Period

For patients who did not undergo allogeneic HSCT, Efficacy follow-up visits for assessment of molecular relapse and until haematological relapse will take place 3-monthly (calculated from cycle 1 day 1) within the first year and 6-monthly within the second year until completion of a 2-year period after treatment with blinatumomab. The following procedures and tests will be performed:

- Physical examination and ECOG performance status
- Vital Signs/Temperature
- Bone marrow aspirate/biopsy
- Routine bloods, U/E, LFTs, LDH, Coagulations screen, FBC (aproximately 30mL of blood)
- Urinalysis
- Recording of anti-leukemic concomitant medication
- Recording of AE possibly related to blinatumomab

For patients who underwent allogeneic HSCT the investigator will contact the patients or his/her treating physician (e.g. via phone) to receive information concerning haematological relapse free and overall survival. Also, information concerning the conditioning regimen, donor type and 100d HSCT related mortality will be collected in the CRF. In addition to the routine collection of adverse events within the core study and until 90 days after last administration of study medication, investigators will report adverse events possibly related to blinatumomab thereafter.

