9.5. Reporting procedures

Death as a result of disease progression and other events that are primary or secondary outcome measures are not considered to be SAEs and should be reported in the normal way, on the appropriate CRF.

The PI (or delegated medically qualified doctor from the trial team) should sign and date the SAE report to acknowledge that he/she has performed the seriousness and causality assessments. Investigators should also report SAEs to their own trust in accordance with local practice.

All SAEs, SARs and SUSARs (excepting those specified in this protocol as not requiring reporting) will be reported immediately (and certainly no later than 24hrs) by the Investigator to the KHP-CTO and CI for review in accordance with the current Pharmacovigilance Policy.

The participant will be identified only by trial number, date of birth and initials. The participant's name should not be used on any correspondence.

It is also required that sites respond to and clarify any queries raised on any reported SAEs and report any additional information as and when it becomes available through to the resolution of the event. Additionally, the KHP-CTO and Amgen may request additional information relating to any SAEs/SARs and the site should provide as much information as is available to them in order to resolve these queries.

Serious Adverse Event (SAE) email address:

[contact]

Adverse events should be reported from the time of signature of informed consent, throughout the treatment period up to, and including 90 days after the participant receives their last dose of the IMP. Serious adverse reactions (such as long-term side effects of trial treatment under investigation) should continue to be reported until the end of follow up.

Adverse events (AE) should be graded using the NCI Common Terminology Criteria for Adverse Events (CTCAE) Version 5.0. The toxicity grades should be recorded on the toxicity part of the CRF.

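### Section 9.9 ends all data collection if the trial stops early, against the protocol's own safety follow-up; the expected 3-year duration is also shorter than its five-year follow-up

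*Protocol*

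**What the plan says.** **Early stop.** Section 9.9 lets the Sponsor, Chief Investigator or regulator discontinue the trial "on the basis of new safety information or for other reasons given by the Data Monitoring & Ethics Committee". In that event, "active participants will be informed and no further participant data will be collected".

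**Safety follow-up.** Section 9.5 has adverse events reported from consent "throughout the treatment period up to, and including 90 days after the participant receives their last dose of the IMP", and the opening of section 9 sets the same window. Section 9.5 also has serious adverse reactions reported until follow-up ends. Section 6.6 deals with a participant who leaves during a serious reaction: information is collected until the reaction is over. Section 10 relies on the visit 90 days after the infusion to assess excessive toxicity.

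**Duration.** Section 6.7 reads: "The trial is expected to take 3 years to complete. The end of trial will be defined as the time of database lock". Section 5.5 sets "efficacy follow-up visits at three, six, nine, 12, 18 and 24 months after treatment start", then telephone follow-up of haematological relapse-free, leukaemia-treatment-free and overall survival "until death or at least until five years after treatment start, whichever occurs earlier". Section 7.3.2 and the footnote to the schedule in section 4.5 run the efficacy visits "until completion of a 2-year period after treatment with blinatumomab", which is a different end point from 24 months after treatment start.

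**Survival endpoints.** Sections 4.3 and 10.2 place the survival analysis at the end of the trial, by Kaplan-Meier.

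**The concern.** Section 9.9 and the safety sections give sites opposite instructions, and the conflict arises when safety data matter most. If the trial stops because of a new risk, patients already exposed would no longer be observed for that risk. The protocol then protects safety data better when one patient leaves than when the whole trial is halted for safety.

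The duration is a separate and smaller conflict. Overall survival is read at the end of the trial, the end of the trial is database lock, and lock is expected before the longest prescribed follow-up could finish. The reader cannot tell whether the final survival analysis is meant to include the telephone follow-up.

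**Working it through.** **1. Early stop: the passages side by side**

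- Section 9.9: after premature discontinuation for any reason, nothing further is collected.
- Sections 9 and 9.5: adverse events to 90 days after the last dose.
- Section 9.5: serious adverse reactions to the end of follow-up.
- Section 6.6: after individual withdrawal, collection continues while a serious reaction lasts.

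For any patient whose last dose was less than 90 days before the stop, or who is still under follow-up, the first rule cannot be obeyed together with the second and third. Section 6.6 concerns individual withdrawal and does not repair section 9.9.

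**2. How long the safety window runs**

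Inputs: up to four cycles; "The duration of one cycle is 6 weeks, including a four week continuous intravenous infusion and a two week infusion free interval"; a possible extension of the interval by at most 7 days (section 5.5); a 90-day window (section 9.5).

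- Last infusion day, four cycles, no delay: 3 × 42 + 28 = day 154. End of adverse event reporting: 154 + 90 = day 244.
- With all three intervals extended by 7 days: 3 × 49 + 28 = day 175, and 175 + 90 = day 265.

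Only the part of this window after the stop date is at risk. Patients with fewer cycles have a shorter window.

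**3. Stage I stop (conditional)**

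The trial does not proceed with 3 or fewer responses among 7 (sections 4.4 and 10.1). The stated design reproduces: at least 4 of 7, then at least 11 of 17, gives a type I error of 0.149 at a 50% rate and power of 0.860 at 75%.

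- True rate 50%: P(X ≤ 3) = (1 + 7 + 21 + 35)/128 = 64/128 = 0.500.
- True rate 75%: P(X ≤ 3) = (1 + 21 + 189 + 945)/16384 = 1156/16384 = 0.071.

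These are the probabilities of a stage I stop. They bear on section 9.9 only if a stage I stop counts as premature discontinuation, which the protocol does not say.

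**4. Trial duration**

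Let A be the accrual time in years. The protocol does not give it, so it is varied here.

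Time needed for every survivor to reach five years = A + 5:

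- A = 0: 5 years
- A = 1: 6 years
- A = 2: 7 years

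Against the stated 3 years the shortfall is A + 2, so at least 2 years even with instantaneous accrual. With a lock at 3 years the last patient would have 3 − A years of follow-up: 2.0 if A = 1, and 1.0 if A = 2.

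For the two-year efficacy visits:

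- Counted from treatment start (section 5.5): A + 2 ≤ 3, so A ≤ 1 year, or 12 months.
- Counted from the end of treatment (sections 4.5 and 7.3.2), for a last patient with four undelayed cycles: 154/365.25 = 0.42 year, so A ≤ 3 − 2 − 0.42 = 0.58 year, or about 7 months.

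**The case against.** Several objections have force.

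- **A stage I stop is a planned outcome of the design, not obviously a premature termination.** This stands. A reader might infer a 50% chance that follow-up is cut off if the drug is inactive. The documents do not support that: nothing says section 9.9 governs a stage I stop, and they give no probability for a stop that it does govern. The 50% and 7% figures are conditional.
- **Three years is an expectation.** This stands too. A reader might infer that the data from years 3 to 5 will be lost, but no lock at month 36 is ordered. No five-year landmark is specified either, and Kaplan-Meier handles unequal follow-up by censoring. The conflict is in the stated duration, and early censoring follows only if the lock does come at 3 years.
- **Molecular relapse-free survival is not part of the 3-versus-5-year gap.** Correct. Marrow assessment ends with the two-year efficacy period, and the later telephone contacts list no molecular test.
- **Not all safety data would be lost.** Correct. Data collected before the stop remain, and day 244 applies to a patient completing four cycles.
- **The number of patients affected is not capped at 17.** Correct. Seventeen counts evaluable patients and withdrawn patients are replaced, so more than 17 could be dosed.

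None of this touches the main contradiction. Section 9.9 has no safety exception, and the protocol shown contains no other clause that supplies one.

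**Conclusion.** The point holds for section 9.9. As written, it cancels safety reporting that sections 9 and 9.5 require, and it is at odds with section 6.6. Its size is whatever falls due after the stop date: adverse event reporting to about day 244 for an undelayed four-cycle patient (day 265 with maximum interval extensions), plus later serious adverse reaction and survival follow-up. This rests only on the wording of those sections and the stated cycle length.

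The duration conflict is real but secondary. The expected 3 years is at least 2 years short of the five-year follow-up whatever the accrual. The 24-month visits fit only with accrual of at most 12 months, or about 7 months under the after-treatment wording. The consequence, if the lock came at 3 years, is earlier censoring of overall survival, not an analysis that cannot be done. This timing conflict leaves the primary endpoint, read on day 29 of cycle 1, and the sample size unaffected.

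**What to change.** 1. **Section 9.9.** Replace the sentence ending data collection. On early termination for any reason, all dosed patients should complete the 90-day safety follow-up, the serious adverse reaction reporting and the survival follow-up that the protocol already requires, unless consent is withdrawn. State that the same applies after a stage I stop, and align the text with sections 9, 9.5 and 6.6.
2. **Section 6.7.** Restate the expected duration and reconcile it with sections 5.5 and 7.3.2 (and the footnote in 4.5), including whether the two-year efficacy period runs from the start or the end of treatment. State whether the final survival analysis comes before or after the five-year telephone follow-up. Either choice is workable; the precise data cut can be left to the SAP.

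The cost is a wording amendment, modest follow-up of a small number of dosed patients after an early stop, and a longer stated trial length. The change to section 9.9 should be in place before the stage I decision, because data not collected after a stop may not be recoverable.

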10.2. Analysis

All patients who have received at least one dose of the trial treatment will be included in the per-protocol analysis. The primary endpoint will be described in numerical terms and as a percentage of all participants. An interim analysis will be performed after 7 patients have been treated, as outlined in section 10.1. Final analysis will be performed at the completion of the trial.

As there are no between-group comparison planned, significance testing is not required. Survival end-points will be assessed at the end of the study, and calculated using the Kaplan-Meier method. AEs and SAEs will be reported as incidences for each patient and each cycle of treatment. The best response attained by each participant throughout the trial will be used to determine the molecular complete remission rate.

There will be no data imputation for missing data in the primary endpoints. Deviations from the initial statistical plan will be described and justified in the report of the trial results.

11. Trial Management Group

Further details of the TMG will be provided in the next version of the protocol.

12. Direct Access to Source Data and Documents

The Investigator(s) will permit trial-related monitoring, audits, REC review, and regulatory inspections by providing the Sponsor(s), Regulators and REC direct access to source data and other documents (e.g. participants' case sheets, blood test reports, X-ray reports, histology reports etc.).

13. Ethics & Regulatory Approvals

The trial will be conducted in compliance with the principles of the Declaration of Helsinki (1996), the principles of GCP and in accordance with all applicable regulatory requirements including but not limited to the Research Governance Framework and the Medicines for Human Use (Clinical Trial) Regulations 2004, as amended in 2006 and any subsequent amendments.

This protocol and related documents will be submitted for review to Health Research Authority (HRA), Research Ethics Committee (REC), and to the Medicines and Healthcare products Regulatory Agency (MHRA) for Clinical Trial Authorisation.

The Chief Investigator will submit a final report at conclusion of the trial to the KHP-CTO (on behalf of the Sponsor) and the REC within the timelines defined in the Regulations. The KHP-CTO or delegate will upload the final report to EudraCT on behalf of the Sponsor

14. Quality Assurance

14.1. Monitoring

Monitoring of this trial will be to ensure compliance with Good Clinical Practice and scientific integrity will be managed and oversight retained, by the KHP-CTO Quality Team.

Investigators should agree to allow trial related monitoring, including audits and regulatory inspections, by providing direct access to source data/documents as required. Participant consent for this will be obtained. Findings generated from on-site and central monitoring will be shared with the Sponsor, CI & PI

14.2. Audits and Inspections

The trial is participant to inspection by MHRA as the regulatory body. The trial may also be participant to inspection and audit by Guy's and St Thomas' NHS Trust under their remit as Sponsor.

The CI or PI organisations/institution(s) will permit trial-related monitoring, audits, REC/ IRB review, and regulatory inspection(s), providing direct access to source data / documents.

The site will inform the KHP-CTO of any MHRA inspections.

15. Data Handling

The Chief Investigator will act as custodian for the trial data. The following guidelines will be strictly adhered to:

- Participant data will be pseudo-anonymised.
- All pseudo-anonymised data will be stored on a secure online data management system.
- All trial data will be stored in line with the Medicines for Human Use (Clinical Trials)
 Amended Regulations 2006 and the Data Protection Act and archived in line with the
 Medicines for Human Use (Clinical Trials) Amended Regulations 2006 as defined in the
 Kings Health Partners Clinical Trials Office Archiving SOP.

16. Data Management

Source data for this trial will comprise the patients electronic medical record (EMR), electronic case report forms (eCRF) and the molecular data held within the trial laboratory. All data are to be stored and transmitted securely in accordance with the General Data Protection Regulation 2016. Data will be managed by the Chief Investigator and aspects of data collection and management may be delegated to nominated deputies including research nurses and clinical research fellows.

17. Publication Policy

It is intended that the results of the study will be reported and disseminated at international conferences and in peer-reviewed scientific journals.

18. Insurance / Indemnity

Non-negligent harm: This trial is an academic, investigator-led and designed trial. The Chief Investigator, local Investigators and coordinating centre do not hold insurance against claims for compensation for injury caused by participation in a clinical trial and they cannot offer any

indemnity. The Association of the British Pharmaceutical Industry (ABPI) guidelines will not apply.

Negligent harm: Where studies are carried out in a hospital, the hospital continues to have a duty of care to a participant being treated within the hospital, whether or not the participant is participating in this trial. Guy's and St Thomas' NHS Trust does not accept liability for any breach in other hospital's duty of care, or any negligence on the part of employees of other hospitals. This applies whether the hospital is an NHS Trust or not. The Sponsor shall indemnify the site against claims arising from the negligent acts and/or omissions of the Sponsor or its employees in connection with the Clinical Trial (including the design of the Protocol to the extent that the Protocol was designed solely by the Sponsor and the Site has adhered to the approved version of the Protocol) save to the extent that any such claim is the result of negligence on the part of the Site or its employees.

All participants will be recruited at NHS sites and therefore the NHS indemnity scheme/NHS professional indemnity will apply with respect to claims arising from harm to participants at site management organisations.

